## Summary of Major Changes in SAP Version

| SAP Version                        | Date      | Section # and Name  | Description of Change   |
|------------------------------------|-----------|---|---|
| V2.0 Based on Protocol Amendment 3 | 22Sep2021 | 3.1 Primary Endpoints
6.3 Safety Analysis                    | AESIs of myocarditis and/or pericarditis were added (in addition to MIS-C).   |
|                                    |           | 3.1 Primary Endpoints   | Seroresponse definition updated to as a change from below the LLOQ to equal or above 4 x LLOQ, or at least a 4-fold rise if baseline is equal to or above the LLOQ.   |
|                                    |           | 4.1 Overall Study Design  | 1. The overall sample size for Part 2 was updated to approximately 12,000 participants.
2. The sample size for Study Arms 8, 10, and 12 were each updated to up to 3,000 participants.
3. The sample size for Study Arms 9, 11, and 13 were each updated to up to 1,000 participants. |
|                                    |           | 4.2 Sample size and Power
4.3 Randomization                  | The overall sample size for each age group was updated to up to 4,000 participants.   |
|                                    |           | 6.6.1 Assay Specific Definition of Seroresponse                 | Definition of assay specific seroresponse is included and updated based on a more conservative approach   |
|                                    |           | 6.8 Data Safety Monitoring Board                                | Included language for the addition of an independent Cardiac Event Adjudication Committee that will adjudicate any suspected cases of myocarditis, pericarditis, or myopericarditis and enable the DSMB to make recommendations to the Sponsor.   |
|                                    |           | 5.4 Immunogenicity Subset
8.5 Appendix E: Schedule of Events | Day 30 (+3 days) blood draw was added to indicate that participants in Cohort D (remainder of the age group) will provide a blood sample at Day 1 and at Day 30 (+3 days)   |
| V3.0 Based on Protocol Amendment 5 | 16Dec2021 | 4.1.2 Part 2, the Blinded Phase                                 | Made updates in figure 2 footnotes to explain that blood sample collection for participants in Cohort D will be prior to randomization and the first dose at Day  |

|                                    |            |  |  |
|------------------------------------|------------|--|--|
|                                    |            |  | 1 and within 4 days of receiving Dose 2 at Day 30 (+ 3 days).  |
|                                    |            | 6.1 General Considerations   | Analysis Period for blinded phase for safety and efficacy analysis   |
|                                    |            | 8.5 Appendix E: Schedule of Events   | Updated footnote #2 in appendix E  |
| V4.0 Based on Protocol Amendment 8 | 06June2022 | 1 Introduction
2 Study Objectives
3 Study Endpoints
4 Study Design      | 
1. Added Part 3 (Study Arm 14) which is the 25 µg dose to be evaluated as an alternative (lower dosing) dosing regimen with a primary series (2 doses) followed by a third dose.
 
2. An optional booster dose for all participants in Part 1(all age groups) and 6 to < 12 year old in Part 2 of the study (10 or 25 µg, depending on age at time of booster) was added.
 |
|                                    |            | 5 Analysis Population  | Updated to clarify the definitions are defined for Part 1 open-label phase and Part 2 blinded phase  |
|                                    |            | 6.6 Long-term Analysis
6.7 Booster Dose Analysis                              | Added to reflect Part 3 and optional booster dose in Protocol Amendment 7. Details will be included in a separate SAP  |
|                                    |            | 8.5 Appendix E: Schedule of Assessments (Parts 1 and 2, Study Arms 1 Through 13) | Updated Appendix header to clarify the schedule of assessments for Part 1 and 2 Arm 1 through 13   |
| V5.0 Based on Protocol Amendment 9 | 28July2023 | 2.1 Primary Objective  | Updated to evaluate the safety of mRNA-1273.214.   |
|                                    |            | 4.1.3 Optional Booster Doses   | 
1. Specified all participants who have not yet received a booster dose will be offered a booster dose with mRNA-1273.214 (instead of mRNA-1273).
 
2. Updated Table 4 to include mRNA-1273.214 in the column titled booster dose.
  |
|                                    |            | 6.5.1.3 Derivation of CDC Case Definition of COVID-19                            | Stated that Covid-19 surveillance (illness visits and convalescent visits) would only be performed while there is still a blinded Part 2 for any age group, after unblinding of trial, this would be discontinued.   |

|  |  |  |  |
|--|--|--|--|
|  |  | 6.9 Interim Analyses                               | Added details for the interim analysis of safety for Part 3 and mRNA-1273.214 booster  |
|  |  | 8.5 Appendix E                                     | Updated to describe changes made to SoA tables   |
|  |  | 6.1 General Consideration                          | Added details that immunogenicity data at Day 57 are analyzed regardless of participant unblinding status.   |
|  |  | 3.1 Primary Endpoints
4.2 Sample size and Power | The P301 comparator in SAP for Part 3 immunogenicity analysis is young adults $\geq 18$ to 25 years of age instead of protocol P301 comparator $\geq 18$ years of age, because the originally planned hypothesis testing in protocol for part 3 will not be performed due to the small number of participants enrolled in Part 3, which is insufficient to power the hypothesis testing. |
|  |  | 6.9 Interim Analyses                               | Added details that additional interim analysis of immunogenicity and safety may be performed after all or subset of participants who receive booster dose have completed BD-Day 29 after the booster dose in an age group for Part 1 and Part 2.   |

## List of Abbreviations

| Abbreviation | Definition                                    |
|--------------|---|
| AB           | antibody                                      |
| AE           | adverse event                                 |
| AR           | adverse reaction                              |
| AESI         | AEs of special interest                       |
| BMI          | body mass index                               |
| bAb          | binding antibody                              |
| BD           | booster dose                                  |
| BLA          | Biologics License Application                 |
| CI           | confidence interval                           |
| CDC          | US Centers for Disease Control and Prevention |
| CEAC         | Cardiac Event Adjudication Committee          |
| CMI          | Cell-Mediated Immunity                        |
| CRO          | contract research organization                |
| CSP          | clinical study protocol                       |
| CSR          | clinical study report                         |
| DHHS         | Department of Health and Human Services       |
| DSMB         | Data Safety Monitoring Board                  |
| eCRF         | electronic case report form                   |
| eDiary       | electronic diary                              |
| EUA          | Emergency Use Authorization                   |
| ELISA        | enzyme-linked immunosorbent assay             |
| FAS          | full analysis set                             |
| GLSM         | geometric least squares mean                  |
| GM           | geometric mean                                |
| GMFR         | geometric mean fold rise                      |
| GMT          | geometric mean titer                          |
| GMR          | geometric mean ratio                          |
| HAART        | highly active anti-retroviral therapy         |
| IgG          | immunoglobulin G                              |
| IP           | investigational product                       |
| IRT          | interactive response technology               |
| IST          | internal safety team                          |
| LAR          | legally authorized representative             |
| LLOQ         | lower limit of quantification                 |
| MAAEs        | medically-attended adverse events             |
| MedDRA       | Medical Dictionary for Regulatory Activities  |
| MIS-C        | multisystem inflammatory syndrome in children |
| mitT         | modified Intent-to-Treat                      |
| mitT1        | modified Intent-to-Treat-1                    |
| mRNA         | messenger ribonucleic acid                    |
| nAb          | neutralizing antibody                         |
| PP           | per-protocol                                  |

| Abbreviation | Definition                                      |
|--------------|---|
| PT           | preferred term                                  |
| PsVNA        | Pseudovirus neutralizing antibody               |
| RT-PCR       | reverse transcriptase polymerase chain reaction |
| SAE          | serious adverse event                           |
| SAP          | statistical analysis plan                       |
| SARS-CoV-2   | severe acute respiratory syndrome coronavirus 2 |
| SAS          | Statistical Analysis System                     |
| SD           | standard deviation                              |
| SoA          | schedule of assessments                         |
| SOC          | system organ class                              |
| SRR          | seroresponse rate                               |
| Study P301   | Study mRNA-1273-P301; NCT04470427               |
| TEAE         | treatment-emergent adverse event                |
| ULOQ         | upper limit of quantification                   |
| WHO          | World Health Organization                       |
| WHODD        | World Health Organization drug dictionary       |

## 1. Introduction

This statistical analysis plan (SAP), which describes the planned analyses for Study mRNA-1273-P204, is based on the most recent approved clinical study protocol (CSP), Version Amendment 9, dated 04-Aug-2022. The most recent approved electronic case report form (eCRF) Version 20.006 dated 31-Jan-2023.

In addition to the information presented in the statistical analysis plan section of the protocol (Section 8) which provides the principal features of analyses for this study, this SAP provides statistical analysis details/data derivations. It also documents modifications or additions to the analysis plan that are not “principal” in nature and result from information that was not available at the time of protocol finalization.

Study mRNA-1273-P204 is a phase 2/3, three-part, open-label, dose-escalation, age de-escalation and randomized, observer-blind, placebo-controlled expansion study to evaluate the safety, tolerability, reactogenicity, and effectiveness of mRNA-1273 SARS-CoV-2 vaccine in healthy children 6 months to less than 12 years of age.

The study will be conducted in 3 parts. Part 1 of the study will be open-label and consist of dose-escalation and age de-escalation in approximately 1,275 participants to select the dose for each age group with the highest number enrolled in the oldest age group. Part 2 of the study will be a placebo-controlled observer-blind evaluation of the selected dose in up to 12,000 participants (up to 4,000 participants each in the 6 years to < 12 years, 2 years to < 6 years, and the 6 months to < 2 years of age groups). Part 3 will be an open-label alternative dosing assessment in approximately 300 participants in the 6 year to < 12 year old age group to assess reactogenicity and immunogenicity of a lower dose regimen.

Per Amendment 7, Part 1 (all ages) and 6 years to < 12 years Part 2 participants will be offered an optional booster dose lower than the chosen primary series for each age group at least 6 months after Dose 2 of mRNA-1273 (Part 1 participants and Part 2 participants in Study Arm 8; Part 2 placebo recipients from Study Arms 9, who crossed over to mRNA-1273 after unblinding). In Amendment 9, all participants in all age groups in Part 1 and Part 2 who have not yet received a booster dose will be offered a booster dose with mRNA-1273.214 (instead of mRNA-1273).

PPD Biostatistics and programming team, designee of Moderna Biostatistics and Programming department, will perform the statistical analysis of the safety, tolerability, reactogenicity, and effectiveness data; Statistical Analysis System (SAS) Version 9.4 or higher will be used to generate all statistical outputs (tables, figures, listings, and datasets).

The SAP will be finalized and approved prior to the primary analysis clinical database lock and treatment unblinding for the study. If the methods in this SAP differ from the methods described in the protocol, the SAP will prevail.

In this document, subject and participant are used interchangeably; injection of IP, injection, and dose are used interchangeably; vaccination group and treatment group are used interchangeably.

A separate SAP will provide more details for part 2 open-label phase, booster doses for part 1 and part 2, and part 3 open-label phase.

## **2. Study Objectives**

### **2.1. Primary Objective**

The primary objectives are the following:

- To evaluate the safety and reactogenicity of up to 3 dose levels (25, 50, and 100 µg) of mRNA-1273 vaccine administered as 2 doses 28 days apart in 3 age groups
- To infer the efficacy of mRNA-1273 (25, 50, and 100 µg, administered as 2 doses 28 days apart) based on immunogenicity in 3 age groups
- To evaluate the safety of mRNA-1273 booster or third dose
- To evaluate the safety of mRNA-1273.214 booster dose
- To infer effectiveness of the mRNA-1273 booster or third dose by establishing noninferiority of Ab response after the booster dose or third dose in children in Study P204 compared with post-primary series in adult recipients of mRNA-1273 in the clinical endpoint efficacy trial (Study P301)

### **2.2. Secondary Objectives**

The secondary objectives are the following:

- To evaluate the persistence of the immune response to mRNA-1273 vaccine (25, 50, and 100 µg)
- To evaluate the incidence of SARS-CoV-2 infection after vaccination with mRNA-1273 or placebo
- To evaluate the incidence of asymptomatic SARS-CoV-2 infection after vaccination with mRNA-1273 or placebo

- To evaluate the incidence of COVID-19 after vaccination with mRNA-1273 or placebo. COVID-19 is defined as clinical symptoms consistent with COVID-19 AND positive RT-PCR for SARS-CoV-2

### **2.3. Exploratory Objectives**

The exploratory objectives are the following:

- To evaluate the genetic and/or phenotypic relationships of isolated SARS-CoV-2 strains to the vaccine sequence
- To describe the ratio or profile of specific S protein bAb relative to nAb in serum
- To characterize the clinical profile and immune responses of participants with COVID-19 or with SARS-CoV-2 infection
- To assess, in a subset of participants, the SARS-CoV-2 S protein-specific T-cell responses
- To explore asymptomatic SARS-CoV-2 infection after vaccination with mRNA-1273 or placebo in participants with serologic evidence of infection at baseline
- To evaluate immune response elicited by the primary series or mRNA-1273 booster dose or third dose of mRNA-1273 against variant(s) of interest

## **3. Study Endpoints**

### **3.1. Primary Endpoints**

The primary safety objective for Part 1 open-label phase or Part 2 blinded phase and open-label phase will be evaluated by the following safety endpoints:

- Solicited local and systemic adverse reactions (ARs) through 7 days after each injection
- Unsolicited adverse events (AEs) through 28 days after each injection
- Medically-attended AEs (MAAEs) through the entire study period
- Serious AEs (SAEs) through the entire study period
- AEs of special interest (AESIs), including multisystem inflammatory syndrome in children (MIS-C) and myocarditis and/or pericarditis, through the entire study period

The primary safety objective of mRNA-1273 booster or third dose will be evaluated by the following safety endpoints:

For mRNA-1273 Booster/Third Dose:

- Solicited local and systemic ARs through 7 days after booster or third dose
- Unsolicited AEs through 28 days after booster or third dose
- MAAEs through the entire study period after booster or third dose
- SAEs through the entire study period after booster or third dose
- AESIs through the entire study period after booster or third dose
- AEs leading to discontinuation from study participation after booster or third dose through the last day of study participation

For mRNA-1273.214 Booster Dose:

- MAAEs through the entire study period after booster dose
- SAEs through the entire study period after booster dose
- AESIs through the entire study period after booster dose
- AEs leading to discontinuation from study participation after booster dose through the last day of study participation

The primary immunogenicity objective for Part 1 open-label phase or Part 2 blinded phase and open-label phase will be evaluated by either:

- The proportion of participants with a serum antibody level at Day 57  $\geq$  antibody threshold of protection. If an accepted serum antibody threshold of vaccine protection against COVID-19 is available, this analysis will form the basis to infer efficacy.
- The GM value of serum antibody level and seroresponse rate from Study P204 vaccine recipients at Day 57 compared with those from young adult ( $\geq 18$  to 25 years of age) vaccine recipients (Day 57) in the clinical endpoint efficacy trial (Study P301). If a threshold of protection is not available, efficacy will be inferred based on establishing noninferiority for each age group (6 years to  $< 12$  years, 2 years to  $< 6$  years, and 6 months to  $< 2$  years in Study P204) compared with 18- to

25-year old participants (Study P301) by both GM value of serum antibody levels and seroresponse rate.

For Part 1 and Part 2, among the two Pseudovirus tests, Pseudovirus Neutralizing Antibody (PsVNA) ID50 and PsVNA ID80 (if applicable), PsVNA ID50 is considered the most appropriate measure of subject response because it falls in the middle of the dynamic range of the dilution response curve while PsVNA ID80 is close to the plateau and thus subject to restriction. The GM and seroresponse rate comparisons between children in P204 and young adults ( $\geq 18$  to 25 years of age) in P301 will be compared for the bAb and nAb measures, with PsVNA (ID50) considered as the primary assay test for the immunobridging.

As a descriptive analysis for Part 3 primary immunogenicity objective with the first two doses of primary series, the GM value of serum antibody level and SRR from Study P204 vaccine recipients at Day 57 will be compared with those for adult ( $\geq 18$  to 25 years of age) vaccine recipients at Day 57 in the clinical endpoint efficacy trial (Study P301). The P301 comparator in SAP for Part 3 immunogenicity analysis is young adults  $\geq 18$  to 25 years of age instead of protocol P301 comparator  $\geq 18$  years of age, because the originally planned hypothesis testing in protocol for part 3 will not be performed due to the small number of participants enrolled in Part 3, which is insufficient to power the hypothesis testing. As a result, all part 3 immunogenicity analysis will be descriptive using P301 comparator ( $\geq 18$  to 25 years), to be consistent with the comparator group in immunogenicity analyses in part 1 and part 2 of the study.

The primary immunogenicity objective to infer effectiveness of the mRNA-1273 booster or third dose will be evaluated by:

- Co-primary endpoints for mRNA-1273 booster in part 1 and 2,
  - GM value of post-booster Ab in Study P204 compared with post-primary series (post-Dose 2) in adults ( $\geq 18$  to 25 years) in Study P301
  - Seroresponse rate of post-booster from baseline (pre-Dose 1) compared with post-primary series (post-Dose 2) from baseline (pre-Dose 1) in the adults ( $\geq 18$  to 25 years) in Study P301, using 4-fold rise definition
- For Part 3, the GM value and SRR of post-third dose Ab in Study P204 compared with post-primary series (post-Dose 2) from young adults ( $\geq 18$  to 25 years of age) in Study P301

Seroresponse due to vaccination at a subject level is defined as a value change from baseline (pre-Dose 1) below the LLOQ to equal or above  $4 \times$  LLOQ, or at least a 4-fold rise if baseline is equal to or above the LLOQ.

There is no primary immunogenicity objective associated with the mRNA-1273.214 booster.

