### **6.3.2. Solicited Adverse Reactions**

An AR is any AE for which there is a reasonable possibility that the test product caused the AE. The term “Solicited Adverse Reactions” refers to selected signs and symptoms occurring after injection administration during a specified post-injection follow-up period

(day of injection and 6 subsequent days). The solicited ARs are recorded by the subject in eDiary. The occurrence and intensity of selected signs and symptoms is actively solicited from the participant during a specified post-injection follow-up period (day of injection and 6 subsequent days), using a pre-defined checklist (i.e., solicited ARs).

The following local ARs will be solicited by the eDiary: pain at injection site, erythema (redness) at injection site, swelling (hardness) at injection site, localized axillary swelling or tenderness ipsilateral to the injection arm, and groin or underarm swelling or tenderness ipsilateral to the side of injection.

The following systemic ARs will be solicited by the eDiary: headache, fatigue, myalgia (muscle aches all over the body), arthralgia (aching in several joints), nausea/vomiting, fever, chills, irritability/crying, sleepiness, and loss of appetite.

The AR categories are different for younger population between Age 37 months to <12 years and Age 6 months to  $\leq$  36 months. Details presented in Table 8 and 9 in the protocol.

The solicited ARs will be graded based on the grading scales presented in Table 8 and 9 in the protocol, modified from the Toxicity Grading Scale for Healthy Adult and Adolescent Volunteers Enrolled in Preventative Vaccine Clinical Trials (DHHS 2007). Investigator will assess Grade 4 events (with exception of fever).

If a solicited local or systemic AR continues beyond 7 days post injection, the participant's parent(s)/ LAR(s) will be prompted to capture details of the solicited local or systemic AR in the eDiary until it resolves or the next IP injection occurs, whichever occurs first.

All solicited ARs (local and systemic) will be considered causally related to injection.

After booster doses with mRNA-1273.214, local or systemic ARs will only be reported on the eCRF if they are medically attended, considered serious or lead to discontinuation from the study. No eDiaries will be used after booster doses with mRNA-1273.214.

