### **3. Study Endpoints**

#### **3.1. Part 2, Open-label Phase**

The study endpoints in Part 2 open-label phase are same as Part 2 blinded phase. Please refer to section 3 in Part 1 open-label phase and Part 2 blinded phase SAP.

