### **6.3.1. Adverse Events**

A treatment-emergent AE (TEAE) is defined as any event occurring during the study not before exposure to study vaccine or any event already present that worsens after exposure to study vaccine. [Note: worsening of a pre-existing condition after vaccination will be reported as a new AE.]

Adverse events will also be evaluated by the investigator for the coexistence of MAAE which is defined as an AE that leads to an unscheduled visit to a healthcare practitioner.

Unsolicited AEs will be coded by PT and SOC using MedDRA and summarized by age and vaccination group, and stage (up to 28 days after any vaccination, follow-up analysis period and overall stage; see [Section 6.1](#) for definitions of vaccination group and stage).

All summary tables (except for the overall summary of AEs) for unsolicited AEs will be presented by SOC and PT for TEAEs with counts of subjects included. SOC will be displayed in internationally agreed order. PT will be displayed in descending order of frequency of total mRNA-1273 group with all dose level combined in Part 1 and in Part 2 correspondingly and then alphabetically within SOC. When summarizing the number and percentage of subjects with an event, subjects with multiple occurrences of the same AE or a continuing AE will be counted once. Subjects will be presented according to the highest severity (the strongest relationship) in the summaries by severity (of related AEs), if subjects reported multiple events under the same SOC and/or PT.

Percentages will be based upon the number of subjects in the Safety Set for specified analysis (long-term analysis or booster/third dose analysis) within each age and vaccination group.

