#### **8.5. Appendix E: Schedule of Assessments for Placebo Recipient Cross-Over Vaccination with mRNA-1273 if any COVID-19 Vaccine is Authorized or Licensed for Participant's Age Group**

| Schedule of Assessments for Placebo Recipient Cross-Over Vaccination                 | Cross-Over D1 | D29 (+ 7) | D36 (+ 3) | D57 (+ 7) | Remainder of Study Visits |
|---|----------------------|------------------------------|------------------|------------------|----------------------------------|
| Days Since Most Recent Injection   |                      | 28                           | 7                | 28               |                                  |
| Study injection (including 30-minute post-dose observation period)                          | X                    | X                            |                  |                  |                                  |
| Safety follow-up call   |                      |                              | X                | X                |                                  |
| Pregnancy test    | X                    | X                            |                  |                  |                                  |
| Recording of unsolicited AEs  | X                    | X                            | X                | X                |                                  |
| Recording of MAAEs and concomitant medications relevant to or for the treatment of the MAAE | X                    | X                            | X                | X                | X                                |
| Recording of SAEs and concomitant medications relevant to or for the treatment of the SAE   | X                    | X                            | X                | X                | X                                |
| Recording of AESIs (eg, MIS-C and myocarditis and/or pericarditis)                          | X                    | X                            | X                | X                | X                                |

Abbreviations: AE = adverse event; AESI = adverse event of special interest; COVID-19 = coronavirus disease 2019; D = day; MAAE = medically attended adverse event; MIS-C = multisystem inflammatory syndrome in children; SAE = serious adverse event.

1. Authorized or licensed in participant's age group.

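### Seven-day solicited reactions are a primary safety endpoint for the Part 2 open-label phase, but the crossover schedule, analysis sets and analysis text make no provision for them

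*SAP*

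**What the plan says.** Section 3.1 of the blinded-phase SAP opens its safety list by stating that the primary safety objective for Part 1 and for "Part 2 blinded phase and open-label phase will be evaluated by the following safety endpoints". The first item is "Solicited local and systemic adverse reactions (ARs) through 7 days after each injection". Section 3.1 of the open-label SAP repeats the scope without exception: "The study endpoints in Part 2 open-label phase are same as Part 2 blinded phase".

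Collection for crossover children is set out in Appendix E of the open-label SAP, the "Schedule of Assessments for Placebo Recipient Cross-Over Vaccination with mRNA-1273". Its safety rows are "Safety follow-up call" (D36 and D57), "Recording of unsolicited AEs" (Cross-Over D1, D29, D36 and D57), and the recording of MAAEs, SAEs and AESIs. It has no row for eDiary activation, eDiary review or solicited reactions.

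For the analysis, section 6.3.1 of the open-label SAP says: "Unsolicited AEs will be coded by PT and SOC using MedDRA and summarized by age and vaccination group, and stage". Section 6.1 of the same SAP names the two long-term vaccination groups as mRNA-1273 and Placebo - mRNA-1273.

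**The concern.** Two things are at stake.

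First, a primary safety endpoint is declared for a phase in which the plan gives no means of measuring or tabulating it. The study report would have to leave the endpoint empty or explain its absence after the fact.

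Second, the long-term tables put two groups side by side whose early reactions were captured differently. A sore arm or fever on Day 2 after mRNA-1273 goes to the solicited tables in the original mRNA-1273 group. After a crossover dose, the schedule offers only adverse-event recording. If such a reaction is recorded there, it enters the unsolicited TEAE percentages of the Placebo - mRNA-1273 group, and could be misread as a safety difference after delayed vaccination.

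**Working it through.** No figure in the plan has to be reproduced. The check sets the endpoint lists against the schedules, analysis sets and analysis text.

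**Step 1: which injections the endpoint covers.** Booster and third doses have their own endpoint lists in section 3.1 of the blinded-phase SAP. Children first randomised to mRNA-1273 receive no further primary-series dose in the open-label phase. For that phase, the injections meant can only be the crossover doses.

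**Step 2: endpoint list against collection schedule.** On the instrument, section 6.3.2 says: "The solicited ARs are recorded by the subject in eDiary".

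| Doses | Schedule | eDiary activation | Solicited reactions among primary endpoints |
|---|---|---|---|
| Parts 1 and 2, original | Blinded-phase SAP, Appendix E | D1, D29 | Yes |
| Part 2 crossover | Open-label SAP, Appendix E | None | Yes |
| mRNA-1273 booster | Open-label SAP, Appendix F | BD-D1 | Yes |
| Part 3 | Open-label SAP, Appendix H | D1, D29, D149 | Yes |
| mRNA-1273.214 booster | Open-label SAP, Appendix J | None | No |

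Only the crossover row is inconsistent. For mRNA-1273.214, section 6.3.2 says openly that eDiaries are not used, and the endpoint list was trimmed to match.

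**Step 3: analysis sets and analysis text (open-label SAP).**
- Section 5.6 defines a Solicited Safety Set for the Part 3 primary series and for the booster or third dose, and none for crossover or long-term analysis.
- Section 6.2.1 lists long-term versions of the FAS, Immunogenicity Subset, PP Immunogenicity Subset, mITT1 Set and Safety Set, but no long-term Solicited Safety Set.
- Section 6.3.2 names only the mRNA-1273 booster and the third dose as injections for solicited analysis.

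Schedule, sets, disposition list and analysis text all agree, so a single table row dropped by mistake is an unlikely explanation. That crossover doses have no eDiary remains an inference, because no sentence states it.

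**Step 4: the long-term display.** Section 5.7 of the open-label SAP pools the two groups in one long-term Safety Set. Section 6.1 starts both on the date of the first mRNA-1273 dose and makes the 28 days after each vaccination the primary safety period. Sections 6.3.1 and 6.3.1.1 give percentages by vaccination group, including treatment-related and medically attended rows. No rule says how a local or systemic reaction after a crossover dose is to be classified.

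**Step 5: what can be sized.**
- Scheduled diary coverage is the injection day plus 6 days, so 7 days per dose and 2 × 7 = 14 days over the two-dose series in the original group. The crossover schedule shows 0.
- Children concerned: three placebo arms of up to 1,000 each, 3 × 1,000 = 3,000. This is a ceiling, since crossover is optional.
- The effect on TEAE percentages cannot be computed, because the SAPs give neither a reaction rate nor the share of reactions that would be reported as adverse events.

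**The case against.** The strongest reply is that the mismatch is a leftover cross-reference in a descriptive part of the study. Section 2.1 of the open-label SAP makes open-label safety descriptive. No success criterion compares the two long-term groups, and section 6.1 of the blinded-phase SAP ends the placebo-controlled safety period before unblinding. The operative text of section 6.3.2 plans no crossover solicited table, and section 6.3.1.1 of the open-label SAP lists crossover adverse events separately. All of this is correct and limits the consequence. It does not remove the contradiction in the endpoint list, and it does not supply the caveat that the side-by-side tables need.

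Three stronger readings are tempting and are not supported:

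- A reader might infer that the unsolicited AE form is the only place a crossover reaction could be recorded. Section 6.3.2 of the blinded-phase SAP also mentions a reactogenicity aCRF. Neither SAP says whether it is used after crossover doses. The crossover schedule also has a safety call at D36, 7 days after the second dose, so follow-up after that dose is not absent. There is no matching call 7 days after the first.
- A reader might infer that the TEAE percentages must differ between the groups by design. If parents do not volunteer reactions, or sites record them elsewhere, the difference could be small or nil.
- A reader might put a number on the shift by multiplying an assumed reaction rate by an assumed reporting share. Assuming 50% and 10% gives 0.5 × 0.1 = 5 points; assuming 90% and 50% gives 0.9 × 0.5 = 45 points. None of these inputs is in the documents. Each product is also an upper limit for its scenario, since section 6.3.1 counts a child once and a child with another TEAE adds nothing to the any-TEAE row.

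**Conclusion.** The point holds in a limited form. The SAPs declare 7-day solicited reactions a primary safety endpoint of the Part 2 open-label phase, while the crossover schedule, analysis sets and analysis text make no provision for them. The endpoint cannot be reported as planned. This rests on reading the crossover schedule as complete, which the other sections support.

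The second part is a possibility, not a demonstrated bias: early reactions can appear as unsolicited, related or medically attended TEAEs in the Placebo - mRNA-1273 group when their counterparts in the original group sit in solicited data. Its size is unknown. The display is descriptive, and the blinded comparison with placebo is untouched. Because the correction is cheap and improves a planned table, it should be made.

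**What to change.** 1. Reconcile section 3.1 of both SAPs with the crossover schedule by removing solicited reactions from the Part 2 open-label endpoints, as was already done for mRNA-1273.214.
2. In the long-term tables of unsolicited, treatment-related and medically attended TEAEs, flag events with onset on Day 1-7 after a dose whose preferred term matches a prespecified list of solicited terms drawn from protocol Tables 8 and 9. Apply the flag to both groups. Medically attended events must be included, because a medically attended reaction has the same asymmetry.
3. Present totals with and without flagged events, and footnote that early reactions were ascertained differently in the two groups.
4. Compare SAEs and AESIs directly, without the flag.

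The cost is SAP wording, one derived flag and one term list, with no new data. The drawback is that some genuine unsolicited events with matching terms will be set apart, which is why both totals should be shown.
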